Preliminary results from 32 heavily pretreated HGSOC patients have been presented at the European Society of Medical Oncology meeting in October 2016, including 7 patients in Cohort 1 (patients with a documented *BRCA* mutation) and 25 patients in Cohort 2 (patients with a negative family history of hereditary breast ovarian cancer syndrome, or negative germline *BRCA* mutation test). Transient grade 4 neutropenia was observed in 69% of patients and resolved to less than or equal to grade 2 within 8 days after onset. Two patients (6%) had febrile neutropenia. Only one patient had dose reduced to 80mg/m². Other toxicities included decreased white blood cell count (78%), anemia (66%), and decreased platelet count (34%). Nonhematologic AEs were generally mild and included fatigue, nausea, vomiting, and diarrhea (9% each). One patient experienced Grade 3 diarrhea and vomiting during infusion.

Among 20 evaluable patients in HGSOC (Cohort 2), there were 7 confirmed PRs, for an ORR of 7 of 20 (35%). Patients had a median of 5 previous therapies (range: 1 to 13). Of the 20 evaluable patients, 15 had platinum-resistant or platinum-refractory disease. Five of 15 patients had a PR for an ORR of 33%. The interim median duration of response is 6 months (3+ to 9 months). The numbers of previous therapies for the responders were 2, 4, 5, 6, and 13. An additional 5 patients with platinum-resistant or platinum-refractory disease had SD \geq 4 months for an overall clinical benefit rate of 66% (10 of 15). Six of 10 patients who had a PR or SD \geq 4 months had received previous bevacizumab. Notably, an expected RR for this patient population with existing agents is approximately 15% (unpublished meta-analysis conducted by Eli Lilly in 2 lines+ ovarian cancer). None of the 6 evaluable patients in Cohort 1 achieved CR or PR, but 4 (67%) achieved SD lasting at least 4 months, for a DCR of 67%. However, our *BRCA* mutant patient cohort, in which all patients received prior PARP inhibitors, did not show response to LY2606368, suggesting CHK1/2 inhibition alone may not reverse the observed PARP inhibitor resistance. **Figure 8** presents a plot of best responses for target lesions by patient, among patients treated with LY2606368.

CC Protocol #: 14-C-0156
 Abbreviated Title: LY Chk1/2 Inhibitor
 Amendment Version Date: 12/02/2020

Abbreviation: *gBRCAm* = germline *BRCA* mutated.

Figure 8. Best response for target lesions by patient, among patients treated with LY2606368

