10 STATISTICAL CONSIDERATIONS

The primary objective of this trial is to establish whether LY2606368 is associated with at least a minimal response rate in participants with BRCA mutation-associated breast or ovarian cancer (cohort 1), HGSOC at low genetic risk (cohort 2), TNBC at low genetic risk (cohort 3), and mCRPC (cohort 4). Note that, effective with amendment I (version date 4/24/2017), Cohort 4 (mCRPC) was closed due to slow accrual. In each of these cohorts, the study will be conducted using an optimal two-stage phase II trial design⁴³ in order to rule out an unacceptably low 5% overall response rate ($p_0=0.05$) in favor of an improved response rate of 25% ($p_1=0.25$). With $\alpha=0.10$ (probability of accepting a poor treatment=0.10) and $\beta = 0.10$ (probability of rejecting a good treatment=0.10), each cohort of this study will initially enroll 9 evaluable participants, and if 0 of the 9 have a response, then no further participants will be accrued in that cohort. If 1 or more of the first 9 participants in a cohort has a response, then accrual would continue until a total of 24 participants have been enrolled in that cohort. As it may take several weeks to determine if a participant has experienced a response, a temporary pause in the accrual to the trial for that cohort may be necessary to ensure that enrollment to the second stage is warranted. If there are 1 to 2 responses in 24 participants, this would be an uninterestingly low response rate. If there were 3 or more responses in 24 participants (12.5%), this would be sufficiently interesting to warrant further study in later trials. Under the null hypothesis (5% response rate), the probability of early termination is 63.0%.

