In the participants enrolled in cohort 6, analyses of biomarkers will be undertaken based on blood samples. As indicated in section 5.1.4, a variety of molecular markers will be collected and evaluated to determine if there are changes in the values after treatment vs. at baseline. For each of the parameters mentioned in section 5.1.4 (CTCs, immune subsets such as Tregs, MDSC, CD8 T+ cells, PD-1, TIM3, CTLA-4, and/or CD40, and γ H2AX and MRE11), values will be obtained at baseline and at C1D15. The change in values between the two timepoints will be determined and assessed for statistical significance in an exploratory fashion. If there are 30 participants with paired values, for a given biomarker, there would be 90% power to detect a difference from baseline with an effect size of 0.75 (0.75 SD of the difference), with a 0.01 two-sided significance level, using a paired t-test. In practice, a Wilcoxon signed rank test will be used if the differences are not normally distributed ($p<0.05$ by a Shapiro-Wilks test). Also, as this will be an exploratory analysis, the significance of the changes will be reported without any formal adjustment for multiple comparisons, but in the context of the number of tests performed.

Several of the molecular markers may also be compared between responders and non-responders in cohort 6 in an exploratory fashion. Assuming that 1/3 of the participants are responders and 2/3 are non-responders, and data are available on 30 of the participants in cohort 6, with data on changes from baseline to cycle 1 day 15 from 10 responders and 20 non-responders, for a given parameter, there would be 87% power to detect a difference between the two groups with an effect size of 1.25 (1.25 SD of the difference), with a 0.05 two-sided significance level, using a two-group t-test. In practice, a Wilcoxon rank sum test will be used if the differences are not normally distributed ($p<0.05$ by a Shapiro-Wilks test). Also, as this will be an exploratory analysis, the significance of the changes will be reported without any formal adjustment for multiple comparisons but in the context of the number of tests performed.

It is expected that 35-40 participants per year may enroll onto this trial. In order to have 143 total evaluable participants, it is anticipated that 4-4.5 years may be required for accrual. To allow for a small number of non-evaluable participants, the accrual ceiling will be set at 153 participants.

CC Protocol #: 14-C-0156

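### Cohorts 1-3: stage 2 ends at 24 enrolled, but the stated power and the 143 total need 24 evaluable participants per cohort

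*Combined protocol and SAP*

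**What the plan says.** All of the design text is in Section 10 (Statistical Considerations) of the combined protocol and SAP.

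- **Cohorts 1-3, aim.** An optimal two-stage design is used to "rule out an unacceptably low 5% overall response rate" in favour of 25%. Alpha is 0.10 ("probability of accepting a poor treatment=0.10") and beta is 0.10.
- **Stage 1.** The count is of evaluable participants: "probability of rejecting a good treatment=0.10), each cohort of this study will initially enroll 9 evaluable participants". A cohort closes if none of the 9 responds.
- **Stage 2.** With at least one response, "accrual would continue until a total of 24 participants have been enrolled in that cohort". One or two responses in 24 participants is called uninteresting; three or more (12.5%) is called worth pursuing. Neither cut-off sentence says evaluable.
- **Cohorts 5 and 6.** The sizes are 36 and 35, both stated as evaluable throughout.
- **Total.** "In order to have 143 total evaluable participants", accrual is projected at 4 to 4.5 years. "To allow for a small number of non-evaluable participants, the accrual ceiling will be set at 153 participants".

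Section 6.3.1 (Definitions) makes enrolled and evaluable different sets. To be evaluable for response, a participant needs measurable disease at baseline, at least one cycle of therapy and a re-evaluation, or else objective progression before the end of cycle 1.

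**The concern.** Within one paragraph the design changes its unit of counting. Stage 1 is measured in evaluable participants, stage 2 in enrolled participants, and the trial total again in evaluable participants. The cut-off of 3 responses was derived for a denominator of 24 response assessments. If accrual stops at 24 enrolled and some of them cannot be assessed, the cut-off stays at 3 while the number of chances to reach it falls. The risk runs in one direction: an active drug is more likely to be set aside than the stated 10%. This is the primary decision rule for three cohorts, so its denominator should not be open to interpretation.

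**Working it through.** **Inputs (Section 10).** p0 = 0.05, p1 = 0.25, n1 = 9, stop if 0 respond, final n = 24, success if at least 3 respond.

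**Formula.** Let X1 ~ Bin(9, p), and let X2 ~ Bin(m - 9, p), where m is the number evaluable at the end of stage 2. Then

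P(not successful) = P(X1 = 0) + P(X1 = 1) x P(X2 <= 1) + P(X1 = 2) x P(X2 = 0).

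**1. Reproduce the plan, m = 24 evaluable.**
- Early termination at 5%: 0.95^9 = 0.630, matching the stated 63.0%.
- At 25%: 0.0751 + 0.2253 x 0.0802 + 0.3003 x 0.0134 = 0.0972, so power is 0.903.
- At 5% the same calculation gives alpha = 0.093.
- A search over two-stage designs with these error limits returns 9/24 as the design with the smallest expected size under 5% (14.5 participants). The stated design is correct for 24 evaluable.

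**2. Which unit the total uses.** 24 + 24 + 24 + 36 + 35 = 143. The plan calls this total evaluable, so each 24 in it is evaluable.

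**3. Follow the stage-2 sentence literally.** Stop at 24 enrolled, keep the cut-off at 3, and let m be the number of those 24 who are evaluable.

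| Evaluable m | Power at 25% | Alpha at 5% |
|---|---|---|
| 24 | 0.903 | 0.093 |
| 23 | 0.897 | 0.086 |
| 22 | 0.889 | 0.079 |
| 21 | 0.880 | 0.073 |
| 20 | 0.868 | 0.066 |
| 19 | 0.853 | 0.059 |

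Example, m = 20 (11 in stage 2): 0.0751 + 0.2253 x 0.1971 + 0.3003 x 0.0422 = 0.1322, so power is 0.868.

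**4. Average over a random number of non-evaluable participants.** Take m ~ Bin(24, 1 - d) and weight the power at each m.

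| Non-evaluable rate d | Source | Average power | Average alpha |
|---|---|---|---|
| 6.5% | Plan's allowance: (153 - 143)/153 | 0.891 | 0.082 |
| 10% | Assumed | 0.883 | 0.077 |
| 18.75% | Interim, upper assumption: 6/32 | 0.855 | 0.063 |

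The last rate comes from Section 1.2. Of 7 Cohort 1 and 25 Cohort 2 patients presented, 6 and 20 were evaluable ("Among 20 evaluable patients in HGSOC (Cohort 2), there were 7 confirmed PRs"). That leaves (7 - 6) + (25 - 20) = 6 of 32. The exact 95% interval is 7% to 36%.

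**The case against.** The best reply is that the intended meaning is plain. The 143 total works only if 24 means evaluable. The same paragraph also uses participants as shorthand: it defines 9 evaluable participants and then calls them the first 9 participants. Section 1.2 reports 25 patients in Cohort 2, so accrual there did not stop at 24 enrolled. All of this stands, and it makes the enrolled wording more likely a slip than a design choice. It does not make the sentence correct, and the stage-2 sentence is the operative stopping instruction.

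A reader might draw four stronger conclusions, which the documents do not support.

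- **The design fails to deliver 90% power.** It delivers 90.3% with the 24 evaluable that the total implies. The loss arises only under the literal enrolled rule.
- **The interim shows that 153 is too few.** The 6 of 32 is from a preliminary cut. The Study Calendar (Section 3.4) starts scans at Cycle 3 Day 1, two 28-day cycles or about 8 weeks in, so some of the 6 may only have been awaiting a first scan. The ceiling is also trial-wide, and a cohort that closes at stage 1 frees places. With one such closure the need is 9 + 24 + 24 + 36 + 35 = 128 evaluable, and 153 tolerates 16.3% non-evaluable.
- **Power in Cohorts 5 and 6 suffers.** Their power rests on 36 and 35 evaluable, stated directly. Nothing in Section 10 makes those cohorts absorb a shortfall elsewhere.
- **Places used by Cohort 4 reduce the margin.** The documents give neither the Cohort 4 enrolment nor whether it counts toward 153.

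**Conclusion.** The stage-2 rule is wrong as written. Its count does not match stage 1, the 143 total or the stated beta. If it is followed literally, power at a 25% response rate falls below the stated 0.90 with the first non-evaluable participant. The expected loss is about 1 percentage point at the plan's own 6.5% allowance and nearly 5 points at 18.75%.

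The result assumes that the cut-off stays at 3, that the first 9 evaluable participants form stage 1, and that response is independent of being evaluable. The 18.75% rate is an upper assumption, not an established one. The type I error is not threatened: alpha only decreases as evaluable participants are lost. The effect is therefore modest and confined to the decision rule of Cohorts 1-3.

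**What to change.** In Section 10, insert the word evaluable before participants in three places: the sentence that ends stage 2 at 24, the sentence on 1 to 2 responses in 24, and the sentence on 3 or more responses in 24. The rule then reads as 24 evaluable participants enrolled, in line with the Cohort 5 and 6 wording and the 143 total.

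The cost is a wording change. At the plan's own allowance it means about 24/(1 - 0.065) = 25.7, so 26 enrolled per cohort, which the 153 ceiling already covers because 143/(1 - 10/153) = 153. No cut-off, error rate or cohort size needs to change.

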Based on the promising results from the HGSOC at low genetic risk cohort 2, the cohort 5 of recurrent platinum-resistant HGSOC will use a single stage design, with an early stopping rule for substantially lower than expected efficacy. A total of 36 evaluable participants will be enrolled in the new cohort in order to have 89% power to rule out a 20% response rate in favor of an alternative response rate of 45%, using a two-tailed 0.05 significance level exact binomial test. In practice, a 95% confidence interval will be formed about the reported proportion of responders, and those with clinical benefit, among the 36 evaluable participants to describe the results obtained. If there are 13 (or more) responders out of 36 evaluable participants (36.1%), the exact two-sided 95% confidence interval about the proportion responding extends from 20.8% to 53.8%, thus ruling out 20% and demonstrating consistency with a result of at least 45%. An early stopping rule will be implemented as follows: if after 10 evaluable participants have been enrolled, there are 0 to 1 responders, then no further participants will be accrued since the upper one-sided 90% confidence bound on 1/10 is 0.337. This would mean that there is a reasonably high probability that the true response rate is below 1/3, obtained previously, and thus the results may not be as promising as expected.

Also, based on the promising results from the HGSOC at low genetic risk cohort 2, the new cohort 6 of non-BRCA mutated HGSOC participants without biopsiable disease will use a single stage design, with an early stopping rule for substantially lower than expected efficacy. A total of 35 evaluable participants will be enrolled in the new cohort in order to have 88% power to rule out a 15% response rate in favor of an alternative response rate of 40%, using a two-tailed 0.05 significance level exact binomial test. In practice, a 95% confidence interval will be formed about the reported proportion of responders, and those with clinical benefit, among the 35

CC Protocol #: 14-C-0156

Abbreviated Title: LY Chk1/2 Inhibitor

Amendment Version Date: 12/02/2020

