evaluable participants to describe the results obtained. If there are 11 (or more) responders out of 35 evaluable participants (31.4%), the exact two-sided 95% confidence interval about the proportion responding extends from 16.9% to 49.3%, thus ruling out 15% and demonstrating consistency with a result of at least 40%. An early stopping rule also will be implemented as follows: if after 10 evaluable participants have been enrolled, there are 0 to 1 responders, then no further participants will be accrued since the upper one-sided 90% confidence bound on 1/10 is 0.337. This would mean that there is a reasonably high probability that the true response rate is below 1/3, obtained previously, and thus the results may not be as promising as expected.

The primary analyses will be done separately by disease cohort, although the response rates may not differ substantially by type of disease. In addition, if results are sufficiently similar, the participants from all four-disease types may be evaluated together in a single cohort in an exploratory fashion. In each cohort, participants will be divided into groups based on whether they responded (PR+CR) or not, or experienced at least some clinical benefit (CR+PR+SD) or not, and when any biologic or biochemical parameters are obtained, the changes in these parameters from baseline will be compared between the two groups using a Wilcoxon rank sum test. As these will be considered exploratory analyses, the results will not be adjusted for any multiple comparisons but will be considered in the context of the hypothesis generating nature of the evaluations. PFI will be estimated using a Kaplan-Meier curve based on all evaluable participants, as well as separately by cohort. The PFI at selected points will also be reported, along with associated 80% and 95% confidence intervals. Safety and toxicity in this population will be determined by tabulating the toxicity grades identified in the participants treated on the trial, by cohort, and describing the findings as needed.

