Other secondary exploratory endpoint for the cohorts 1-3 and 5 will focus on the ability of biochemical changes in the DNA damage repair and cell cycle checkpoint pathways to be associated with response. This will be evaluated in a descriptive fashion. For cohort 5, all participants will undergo a biopsy at baseline. It is expected that 12 participants may be clinical responders and that perhaps 6 to 12 more may have clinical benefit. Beginning at the first time after which a tumor grows >15% over baseline, among those who have responded or shown clinical benefit by 4 months, a second biopsy at progression will be obtained to provide potential resistance mechanisms. For a potential single protein or gene biomarker, with 16 paired biopsies available, there would be 80% power to detect a change from baseline with an effect size of 0.75 (0.75 SD of the change) which would be significant at the 0.05 two-tailed significance level using a paired t-test. Similarly, 15 paired biopsies would result in 94% power to detect a change with a 1.0 SD effect size, while 10 paired biopsies would have 80% power for a 1.0 SD effect size, both with a 0.05 two-tailed significance level. If there were 3 total potential protein or gene biomarkers instead of one, 22 paired biopsies would yield 81% power for a 0.75 SD effect size using a two-tailed 0.017 significance level paired t-test in order to permit adequate participants for a very strict Bonferroni adjustment, holding the three tests to an overall 0.05 significance level, while 14 paired biopsies would have 81% power for detecting a 1.0 SD effect size, also at the 0.017 significance level. In practice, a Wilcoxon signed rank test will be used instead of a paired t-test if the changes are not

CC Protocol #: 14-C-0156

Abbreviated Title: LY Chk1/2 Inhibitor

Amendment Version Date: 12/02/2020

normally distributed ($p<0.05$ by a Shapiro-Wilks test). Also, if multiple markers are being evaluated, a Hochberg adjustment may be used instead of an overly conservative Bonferroni correction.

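### Cohorts 5 and 6: the stated 89% and 88% power leave out the early stop at 0–1 responders in 10; with it, power is 88.1% and 86.2%

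*Combined protocol and SAP*

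**What the plan says.** Section 10 (Statistical Considerations) describes cohorts 5 and 6 as single-stage designs that carry an early stopping rule for low efficacy.

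- **Cohort 5**, 36 evaluable participants: "89% power to rule out a 20% response rate in favor of an alternative response rate of 45" per cent, by an exact binomial test at the two-sided 5% level. The bar: "If there are 13 (or more) responders out of 36 evaluable participants (36.1" per cent), at which the exact 95% interval (20.8% to 53.8%) excludes 20%.
- **Cohort 6**, 35 evaluable participants: "88% power to rule out a 15% response rate in favor of an alternative response rate of 40" per cent, same test. The bar: "If there are 11 (or more) responders out of 35 evaluable participants (31.4" per cent), at which the interval (16.9% to 49.3%) excludes 15%.
- **Stop, worded identically for both**: "if after 10 evaluable participants have been enrolled, there are 0 to 1 responders, then no further participants will be accrued".

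No power or error rate is given with the stop included.

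On combining cohorts, Section 10 makes the primary analyses separate by disease cohort. The one response pooling it mentions is exploratory and conditional: "if results are sufficiently similar, the participants from all four-disease types may be evaluated together in a single cohort". Section 1.2 (Background and Rationale) describes cohort 6 as cohort 5's population except that disease cannot be biopsied, and gives both cohorts an efficacy purpose.

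**The concern.** A futility stop can only remove paths to success. A cohort that starts with 0 or 1 responder in 10 could still have reached its bar by the end, and the stop forbids that. If the stop is firm, and its wording is, the power of the written design must be below that of the single-stage test. The quoted 89% and 88% would then describe a design slightly different from the one that will be run.

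At stake is the accuracy of two published operating characteristics. The validity of the bars and the adequacy of the sample sizes are not in question.

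A second, lesser matter is that two cohorts drawn from nearly the same population, both meant to inform efficacy, have no planned combined response estimate. That costs some precision.

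**Working it through.** **Inputs (all from Section 10).** Cohort 5: n = 36, p0 = 0.20, p1 = 0.45, bar r = 13. Cohort 6: n = 35, p0 = 0.15, p1 = 0.40, bar r = 11. Both: stop if X₁ ≤ 1 among the first 10.

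**Step 1: reproduce the plan's figures without the stop.** Power = P(X ≥ r), with X ~ Bin(n, p1).

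- Cohort 5: P(X ≥ 13 | 36, 0.45) = 0.8933. Stated 89%.
- Cohort 6: P(X ≥ 11 | 35, 0.40) = 0.8877. Stated 88%, apparently truncated.

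The upper tails at the null are 0.0182 (cohort 5, 20%) and 0.0110 (cohort 6, 15%), both under 0.025. One responder fewer gives 0.0424 (12/36) and 0.0292 (10/35), so 13 and 11 are the correct bars. The exact intervals for 13/36 and 11/35 also reproduce, as does the upper one-sided 90% bound of 0.337 on 1/10.

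**Step 2: include the stop.** Power with stop = Σ over x = 2,…,10 of P(X₁ = x) × P(Y ≥ r − x), with X₁ ~ Bin(10, p1) and Y ~ Bin(n − 10, p1). Equivalently, subtract the paths that begin with 0 or 1 responder and would still have reached the bar.

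| | Cohort 5 | Cohort 6 |
|---|---|---|
| Path with X₁ = 0 | 0.0025 × 0.3743 = 0.0009 | 0.0060 × 0.4142 = 0.0025 |
| Path with X₁ = 1 | 0.0207 × 0.5287 = 0.0110 | 0.0403 × 0.5754 = 0.0232 |
| Total lost | 0.0119 | 0.0257 |
| Power with stop | 0.8933 − 0.0119 = **0.8814** | 0.8877 − 0.0257 = **0.8620** |
| Below the stated value | 89 − 88.1 = 0.9 points | 88 − 86.2 = 1.8 points |

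**Step 3: false-positive rate.** The same sum at the null gives 0.0175 (cohort 5, 20%) and 0.0101 (cohort 6, 15%). Both are slightly below their single-stage values.

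**Step 4: what a combined estimate would add.** Exact (Clopper-Pearson) 95% intervals for illustrative results near 1/3:

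| Result | Interval | Width (points) |
|---|---|---|
| 12/36, cohort 5 alone | 18.6–51.0% | 32.4 |
| 11/35, cohort 6 alone | 16.9–49.3% | 32.4 |
| 23/71, both at full size | 21.8–44.5% | 22.8 |
| 13/46, one cohort stopped at 1/10, the other 12/36 | 16.0–43.5% | 27.5 |

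The 23-point width is a best case. At a true rate of 1/3, each cohort stops early with probability 10.4%, so at least one does with probability 1 − 0.896² = 19.7%.

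**The case against.** The plan attributes its power to the exact binomial test, and for that test both figures are right. The stop is described openly in the same paragraph, the gap is under two points, the error rate falls, and no number of patients or bar would change. All of this stands and is why the point is minor. It does not make 89% and 88% properties of the design with a firm stop.

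On combining the cohorts, separate primary analysis is a legitimate choice. Non-biopsiable disease may differ in lesion type, the null rates differ, and Section 10 already allows some exploratory pooling and a progression-free interval curve over all evaluable participants. Anyone could also add the two reported counts. This stands too, so the combined estimate can only be an optional addition.

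Three stronger readings are tempting, and the documents do not support them.

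- **That the cohorts are underpowered because Section 10 elsewhere works from about one third.** The stopping-rule text refers to "the true response rate is below 1/3, obtained previously", and for cohort 5's biopsy numbers "It is expected that 12 participants may be clinical responders", that is 12/36. But there 1/3 serves as a futility reference and a biomarker planning assumption. It is not the efficacy alternative, and powering at a target rate is legitimate. It also rests on 5 of 15 patients (exact 95% interval 11.8% to 61.6%), which is compatible with both 40% and 45%.
- **That the two bars judge similar results inconsistently**, since 12/36 would not exclude 20% while 11/35 would exclude 15%. This only reflects different null rates. The lower limit for 11/35 is 16.9%, so it would not exclude 20% either.
- **That the missing combined analysis is an error.** Nothing in the plan requires one.

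**Conclusion.** The point holds as a small overstatement. With the stop included, power is 88.1% for cohort 5 and 86.2% for cohort 6, against a stated 89% and 88%. The bars of 13/36 and 11/35 remain valid at one-sided error rates of 1.75% and 1.01%, and the sample sizes need no change.

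This assumes that the stop is binding, that it is applied to the first 10 evaluable participants, and that a stopped cohort cannot meet its bar. If the sponsor regards the stop as advisory, the single-stage figures of 89.3% and 88.8% apply, and the text should say so.

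The absence of a cohort 5 + 6 response estimate is a missed opportunity for precision only.

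**What to change.** **Recommended.** In Section 10, restate power with the stopping rule included: about 88% for cohort 5 (20% against 45%) and about 86% for cohort 6 (15% against 40%). Keep n = 36 and n = 35, the two bars and the stop. The only cost is a slightly less favourable stated figure.

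**Optional.** Add one supplementary analysis: the combined cohort 5 + 6 response rate with an exact 95% interval, on whatever number is evaluable, shown beside the separate primary results. State that it is not a success bar and that its interval is not adjusted for the early stop. Label it post hoc if response data have already been seen. It costs no patients and changes no primary analysis. Its drawbacks are that it mixes biopsiable with non-biopsiable disease and that the gain in precision shrinks if a cohort stops early.
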